4 TREATMENT PROCEDURES

4.1 Study plan

The observation will begin after the subjects have signed the informed consent form. PrEP treatment should then be initiated when the HIV antibody/antigen test (4th generation test) taken at the first visit is confirmed negative.

However, the window period to rule out HIV infection is 12 weeks. It is not desirable that participants are undergoing HIV seroconversion when they commence PrEP, however the study population is per definition at high-risk for HIV acquisition. It is likely that the majority of the participants will not be in a position to abstain from sex or use condoms effectively for a 12 week period. Therefore it is NOT recommended to delay PrEP pending a negative HIV test results 12 weeks from the last high risk exposure. International and national guidelines do not recommend delaying PrEP initiation in this high risk group for HIV acquisition. Per definition, those in need for PrEP are at high risk for HIV acquisition justifying PrEP initiation even at first visit.

For those who have had high risk exposure within 14 days prior to screening, a HIV-DNA provirus test should be requested and the serum test for HIV should be repeated at 2 weeks, 4 weeks and 8 weeks and 12 weeks from the day they commenced PrEP.

Subjects that have already commenced PrEP treatment can be included in the study. These subjects will be requested to consent to collection of historical medical information from the date when the PrEP treatment was initiated.

Follow-up visits are according to clinical practice, clinical judgement and standard patient management described in SmPC. For those outside the window period for HIV infection a standard visit at 4 weeks and 12 weeks post initiation of PrEP and thereafter every 3 months during the PrEP treatment for 24 months. Where clinically indicated the subject may attend the clinic between 3 months' follow-up visits. Data from these visits will be collected as Extra Clinical Visits.

4.2 Variables

Subjects will be treated according to local prescribing information and clinical judgement and assessments performed according to site clinical practice. The inclusion period will last from final approval from The Regional Ethical Committee and until end of 2018.

Data on demographics, sexual health including sexual behaviour, HIV infection status, STIs, compliance and recreational drug use will be collected at the baseline visit, 3 months' follow-up visits, end of study visit and relevant extra visits. HIV-tests will also be taken at weeks 2, 4 and 8 in order to identify people in the seroconversion phase at inclusion to reduce risk of development of drug resistance. For subjects at particular high risk for HIV infection prior to PrEP treatment, HIV-DNA provirus testing will be assessed at the first visit according to the doctor's clinical judgement. As a measure of adherence blood samples will be drawn and the tenofovir disoproxil fumarate (TDF) concentration in plasma will be measured as well as a self-reported drug protocol.

Investigators are asked to report the requested data in the electronic Case Report Form (eCRF).

Table 1 Data collection and visit structure

Study Visits ¹	Visit 0 (evaluation)	Visit 1(start of treatment)	Visit 2 (week 2)	Visit 3 (week 4)	Visit 4 (week 8)	Follow-up visits (approx. every 3 months)	Extra visits	End of study visit (24 months after start of treatment)
Clinic visits	x			x		x ¹	x	x
Informed consent	X							
Assess eligibility criteria	x	x						
Demography	X							
HIV test ²	x		x	x	x	x	x ³	x
HIV-DNA provirus ⁴	x ⁴	x ⁴						
History of STI	x							
STI screening	x					x	x ³	x
Bloodsample for TFV-PD plasma concentration				x		x ⁵	x ^{3,5}	x ⁵
Questionnaire sexual behaviour (start of treatment)	x					x		x
Questionnaire sexual behaviour (follow-up)	x					x		x
Compliance				x		x	x	x
Adverse events				x		x	x	x
Subject diary				x		x		x

¹ clinic visits to be schedule to fit with PrEP treatment guidelines and local clinical practice. At each visit assessments as indicated in table should be captured in the database if they are conducted.

² If a subject is infected with HIV during PrEP treatment resistance of the HIV virus for emtricitabine and tenofovir disoproxil fumarate should be checked.

³ If clinically indicated

⁴ If high risk sexual contact within the last 14 days

⁵ only applicable for subject on continuous PrEP treatment

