		
alcohol use.
 
Subject will be screened for the following STIs during the enrolment visit: HIV, syphilis, hepatitis A/B/C, Chlamydia trachomatis, Neisseria gonorrhoea, and Mycoplasma genitalium.
 
Participants will be asked to return approximately one week later to discuss their HIV result and whether they wish to proceed with initiation of PrEP.
 
The decision regarding initiation of continuous or intermittent PrEP is based on a discussion with the subject and study team (doctor/nurse), subjects' personal preference, medical considerations and whether the expected use will surpass more than 15-20 tablets of FTC/TDF per month.
 
HIV testing will be repeated at 2, 4 and 8 weeks from the most recent high risk exposure (for HIV acquisition) prior to initiation of PrEP. Thereafter participants are requested to visit the clinic every 3 months from PrEP initiation (for the next 24 months) for HIV & STI testing, evaluation of compliance (blood test for drug monitoring in continuous PrEP arm, drug diaries in both continuous and intermittent PrEP arms), assessment of clinical and/or biochemical adverse reactions and quality of life and sexual behaviour assessment. Subjects will be asked to answer the same questions regarding sexual behaviour and quality of life at follow up visits as at inclusion study visit.

Statistics	Sample size	Not applicable
	Methods	Categorical variables will be described by means of absolute and relative frequencies, while continuous variables by means of mean, standard deviation, quartiles, min and max.

LIST OF ABBREVIATIONS

AE	Adverse Event
ART	Anti retroviral therapy
COHP	Country of high prevalence of HIV
CRA	Clinical Research Associate
CRF	Case Report Form
CSR	Clinical Study Report
CT	Chlamydia trachomatis
DM	Data Manager
EC	Ethics Committee
eCRF	Electronic Case Report Form
EDC	Electronic Data Capture
EMA	The European Medicines Agency
GCP	Good Clinical Practice
HIV	Human Immunodeficiency Virus
ICF	Informed Consent Form
ICH	International Conference on Harmonisation
IMP	Investigational Medicinal Product
ISF	Investigator Site File
ITT	Intention-To-Treat
MG	Mycoplasma genitalium
MSM	Men who have sex with men
NG	Neisseria gonorrhoea
PI	Principal Investigator
PIS	Patient Information Sheet
PrEP	Pre-Exposure Prophylaxis
SAE	Serious Adverse Event
SD	Standard Deviation
SDV	Source Data Verification
SUSAR	Suspected Unexpected Serious Adverse Reaction
STI	Sexually Transmitted Infections

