1.1 Aim of Present Study

The main objective of this study is to monitor the impact of PrEP on the subject's psychological and sexual health. It is also important to monitor the adherence to PrEP, development of drug resistance (in the case of undetected HIV infection at initiation of PrEP), frequency of other STIs, changes in sexual behaviour, recreational drug use and quality of life. PrEP has proven to be effective in reducing the sexual acquisition of HIV, however this requires that the medication is taken as prescribed, whilst the subject is exposed to high risk of infection.

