3.5 Subject Withdrawal

In accordance with the Declaration of Helsinki, the Investigator must explain to the subject that they have the right to withdraw from the study at any time, and that this will in no way prejudice their future treatment. The reason for any kind of withdrawal should be recorded on the appropriate CRF.

If a subject is proven HIV positive when using PrEP, the treatment should be stopped immediately to prevent development of resistance, registered as a PrEP failure, and referred to the Dept. of Infectious Diseases for regular follow-up of their HIV infection and checked for resistance to tenofovir disoproxil fumarate and emtricitabine (as is already standard clinical practice).

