7.4 Missing data

Subjects missing data values will not be excluded from the analysis, but their data will not be replaced; frequency of missing data will be given for all analysed variables.

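### No questionnaire is planned when a subject stops PrEP or leaves the study, and by-time-point summaries will drift towards those who stayed on PrEP

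*Protocol*

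**What the plan says.** Section 1.1 of the protocol sets the aim: "The main objective of this study is to monitor the impact of PrEP on the subject's psychological and sexual health". The instrument is a repeated questionnaire. The protocol outline (Methods & procedures) states: "Subjects will be asked to answer the same questions regarding sexual behaviour and quality of life at follow up visits as at inclusion study visit".

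- **Closing visit.** Table 1 in section 4.2 has a single closing column, "End of study visit (24 months after start of treatment". There is no column for early stop of PrEP or for withdrawal.
- **Routine visits.** Section 4.1 schedules visits at weeks 4 and 12 and "thereafter every 3 months during the PrEP treatment for 24 months".
- **Withdrawal.** Section 3.5 says: "The reason for any kind of withdrawal should be recorded on the appropriate CRF". It attaches no questionnaire.
- **Extra visits.** The text of 4.2 says that data on sexual health and behaviour, among others, "will be collected at the baseline visit, 3 months' follow-up visits, end of study visit and relevant extra visits". Table 1 leaves the row "Questionnaire sexual behaviour (follow-up" and its start-of-treatment companion blank under extra visits. Adverse events and compliance are ticked there.
- **Analysis.** Section 7.2 limits the description to enrolled people on PrEP. Section 7.3 summarises by time point, using the closest measurement. Section 7.4 keeps subjects with missing values in the analysis, says that "their data will not be replaced", and promises counts of missing values.

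The SAP carries the same text on these points in its sections 1.1, 3.5, 4.1, 4.2 and 7.2 to 7.4.

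**The concern.** Subjects serve as their own controls (sections 3.1 and 3.3), so the main objective rests on before-and-after comparison. In such a design, a change in who answers can look like a change in behaviour or well-being. Stopping PrEP is plausibly linked to tolerability, mood or altered sexual risk, which are close to what the questionnaire measures.

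Two things are at stake. First, a subject who stops at month 5 has a last planned questionnaire at month 3, so the questionnaire data for the period leading to the stop may not exist, and no later model can recover them. Second, the summaries compare baseline values from everyone with later values from those still attending, and the plan contains no analysis of who has left.

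**Working it through.** The documents give no sample size, discontinuation rate or primary time point, so there is no figure to reproduce. The check has a textual part and an illustrative part.

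**Which planned contact would yield a questionnaire at or after a stop?**

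1. A routine 3-monthly visit: section 4.1 ties these to being on PrEP, so none clearly applies after a stop.
2. An extra visit: the text of 4.2 suggests yes, Table 1 says no.
3. Withdrawal: a reason only.
4. The month-24 visit: counted from start of treatment, so a stopper could attend. Nothing says that they will be asked to, and nothing bars it.

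So no questionnaire is tied to the stop, and whether one follows later is left to each site.

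**How selected could later time points become?** Assume a constant probability q of stopping before each of 8 quarterly questionnaires (months 3 to 24), and none completed afterwards. The share answering at visit k is (1 − q)^k. The expected number per starter is the sum S of these shares over k = 1 to 8. The part of S that comes from people who stop before month 24 is [S − 8(1 − q)^8] / S.

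| q (assumed) | At least one follow-up questionnaire | Month-24 questionnaire, (1 − q)^8 | S | Share of follow-up questionnaires from early stoppers |
|---|---|---|---|---|
| 2% | 98% | 85.1% | 7.31 | 6.9% |
| 5% | 95% | 66.3% | 6.40 | 17.0% |
| 10% | 90% | 43.0% | 5.13 | 32.8% |

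Early stoppers are therefore present in the data but thin out over time.

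**What can that do to a summary?** There are two separate effects.

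*Change of mix.* Assume stayers average 10 partners, stoppers 6, and nobody changes. With a share p stopping, the baseline mean is 10(1 − p) + 6p:

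- p = 0.2: 9.2, against 10 later, an apparent rise of 0.8
- p = 0.3: 8.8, an apparent rise of 1.2
- p = 0.4: 8.4, an apparent rise of 1.6

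If change is taken within the same subjects, all three rises become 0.

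*Different change in those who left.* Let d be the share who stopped and D the stayer-minus-stopper difference in mean change, in SD units. The mean change in all enrolled equals the stayers' mean change minus dD, so a stayers-only summary is off by dD:

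- d = 10%, D = 0.2: 0.02 SD
- d = 30%, D = 0.5: 0.15 SD
- d = 50%, D = 0.8: 0.40 SD

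A within-subject summary does not remove this second effect. Only data from stoppers can reduce it. All values of q, p, d, D and the partner counts are assumptions.

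**The case against.** The strongest reply is that the study is descriptive, follows clinical practice, and already collects a good deal from people who stop. Much of this stands, and it rules out several stronger readings.

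- A reader might infer that the main result describes only those who stayed on PrEP. It does not. The questionnaire is given at baseline and every 3 months, stoppers answer until they stop, and section 7.4 does not exclude them. No document names month 24, or any visit, as the main time point.
- A reader might infer that stoppers are shut out of the closing visit. The visit is counted from start of treatment, and section 8.4 treats consent and treatment as separate matters. The documents are silent here, not exclusionary.
- A reader might infer that the experience leading to a stop is never recorded. The withdrawal reason is recorded, adverse events and compliance are ticked at extra visits, and section 6 lists reasons for poor compliance. What is not clearly planned is the questionnaire.
- The partner-count illustration vanishes under the own-control comparison of section 3.1. That is correct, but section 7.3 specifies no paired summary, so the analysis as written is exposed to it.
- Counts of missing values will show that numbers fall. They will not show who left or in which direction the summary moves.
- Section 7.1 defers detail to a separate SAP, but the SAP supplied repeats the protocol on these points. An analysis plan also cannot supply a questionnaire that was never completed.

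**Conclusion.** The point holds in this form: no questionnaire is planned at stop of PrEP or at withdrawal, the two statements about extra visits disagree, and the planned summaries let later time points, month 24 most of all, mainly reflect people who stayed on PrEP. This is a weakness in the evidence for the main objective that should be corrected. It does not invalidate the study.

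The size cannot be determined from the documents. Under the assumed rates, 43.0% to 85.1% of starters would supply a month-24 questionnaire, and a stayers-only mean change would be off by 0.02 to 0.40 SD. This rests on stoppers giving no later questionnaire and on their change differing from that of stayers. If stopping is rare or unrelated to the outcomes, the effect is small.

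**What to change.** 1. **Table 1.** Add a questionnaire, adverse-event and compliance assessment at stop of PrEP or study withdrawal, consent permitting, with the app allowed. State that it comes in addition to the remaining 3-monthly and month-24 questionnaires for stoppers who stay in the study. A closing visit at whichever comes first would be the wrong change, because it could remove the month-24 questionnaire that the present wording leaves open to stoppers. Define what counts as a stop, for data collection only, in intermittent users.
2. **Section 4.2.** Reconcile the text on extra visits with the blank questionnaire cells in Table 1.
3. **Sections 7.2 and 7.3, protocol and SAP.** State that stoppers' data stay in the analysis. Summarise change from baseline within the same subjects at each time point. Tabulate baseline and last questionnaire values for stoppers beside those who completed 24 months.

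The cost is one extra questionnaire per stopper, on forms that already exist, and one extra table. People who withdraw consent or stop attending will still be missing, and the table will at least show how they differed at baseline.

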4.3 Adverse Events and Serious Adverse Events

4.3.1 General

The Investigator should ask the subject questions during the clinic visits in order to ensure that appropriate adverse event information is recorded in the subject's source notes and is then subsequently entered into the CRF. Adverse events will be recorded in response to the following question - "Since you were last asked have you felt unwell or different from usual in any way?" All relevant responses from the subject will be recorded in the CRF on an adverse

event form and graded on severity, seriousness and relationship to study medication. For further details regarding the classification of adverse events see below.

Subjects will be questioned regarding any signs and symptoms occurring in the screening period and for baseline signs and symptoms prior to the first dose of study medication on Day 1. Subjects will subsequently be questioned regarding adverse events throughout the study. All adverse events are to be reviewed by the Investigator while on-going and subsequently documented at the point of resolution. All adverse events classified as serious are to be immediately brought to the attention of the Investigator by site staff for review and action in accordance with Section 4.4.5 below.

All on-going adverse events will be followed up by the Investigator until subject discharge or resolution. Additional clinic visits may be scheduled by the Investigator to follow-up on adverse events according to their clinical judgement.

4.3.2 Seriousness

- Adverse Events (AE): any untoward medical occurrence in a subject or clinical trial subject administered a medicinal product and which does not necessarily have a causal relationship with this treatment. This includes clinically significant laboratory abnormalities as judged by the Investigator.
- Serious Adverse Events (SAE) are defined as: any untoward medical occurrence or effect that at any dose results in death, is life-threatening, requires hospitalisation or prolongation of existing hospitalisation, results in persistent or significant disability or incapacity, or is a congenital anomaly or birth defect. Events otherwise considered serious by the Investigator should also be reported as SAEs. Malignancy would in most cases fall into that category. The medical occurrence or effect does not need to be related to the study medication.

4.3.3 Severity

Severity is classified according to the Common Terminology Criteria for Adverse Events (CTCAE v.4.03):

Grade 1	Mild; asymptomatic or mild symptoms; clinical or diagnostic observations only; intervention not indicated.
Grade 2	Moderate; minimal, local or non-invasive intervention indicated; limiting age-appropriate instrumental ADL.
Grade 3	Severe or medically significant but not immediately life-threatening; hospitalization or prolongation of hospitalization indicated; disabling; limiting self care ADL.
Grade 4	Life-threatening consequences; urgent intervention indicated.
Grade 5	Death related to AE.

4.3.4 Relationship to study medication

- Unrelated: This category is applicable to those adverse events which, after careful medical consideration at the time of evaluation, are judged to be clearly and incontrovertibly due to extraneous causes (disease, environment, etc.) and do not meet the criteria for study medication relationship listed under remote, possible or probable.
- Unlikely: In general, this category is applicable to those adverse events that, after careful medical consideration at the time they are evaluated, are judged to be remotely related to the test study medication. An adverse event may be considered remote if, or when, for example: (i) it does not follow a reasonable temporal sequence from administration; (ii) it could readily have been produced by the subject's clinical state, environmental or toxic factors, or other modes of therapy administered to the subject; (iii) it does not follow a known response pattern to the suspected study medication; (iv) it does not reappear or worsen when the study medication is re-administered.
- Possible (must have first two criteria): This category is applicable to those adverse events which, after careful medical consideration at the time they are evaluated, the connection with the test study medication administration appears unlikely but cannot be ruled out with certainty. An adverse event may be considered possible if, or when: (i) it follows a reasonable temporal sequence from administration; (ii) it could readily have been

produced by the subject's clinical state, environmental or toxic factors, or other modes of therapy administered to the subject; (iii) it follows a known response pattern to the suspected study medication; (iv) it does not reappear or worsen when the study medication is re-administered.

- Probable (must have first three criteria): This category is applicable to those adverse events, which, after careful medical consideration at the time they are evaluated, the connection with the test study medication administration appears to, with a high degree of certainty, be related to the test study medication. An adverse event may be considered probable if: (i) it follows a reasonable temporal sequence from administration; (ii) it could not be reasonably explained by the known characteristics of the subject's clinical state, environmental or toxic factors, or other modes of therapy administered to the subject; (iii) it disappears or decreases on cessation or reduction in dose. There are important exceptions when an adverse event does not disappear upon discontinuation of the study medication, yet study medication-relatedness exists; e.g. bone marrow depression, fixed study medication eruptions, and tardive dyskinesias; (iv) it follows a known response pattern to the suspected study medication; (v) it reappears upon rechallenge.
- Not assessable: When it is not possible to assign the event to any of the criteria above categories.

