4.3.5 Serious adverse reactions and unexpected adverse reactions

Definitions

Adverse Reaction: all untoward and unintended responses to an investigational medicinal product related to any dose administered.

Unexpected adverse reaction: an adverse reaction, the nature or severity of which is not consistent with summary of product characteristics for Truvada® (http://www.ema.europa.eu/docs/no_NO/document_library/EPAR_-_Product_Information/human/000594/WC500043718.pdf).

Suspected Unexpected Serious Adverse Reaction (SUSAR): any serious adverse reaction that might be related to the study medication and is unexpected according to the definition above.

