6 VARIABLES

- Demographic information (age, gender, race, height, weight, sexuality, education, work situation, relationship status)
- Sexual behaviour (number of partners, condom use, HIV positive partners)
- Sexual transmittable infections (history and current status for infections with syphilis, hepatitis A/B/C, *Chlamydia trachomatis*, *Neisseria gonorrhoea*, and *Mycoplasma genitalium*).
- Compliance (days tablets taken, days tablets missed, compliance (%), compliance in connection with exposure to infection, reason for poor compliance, serum concentration of FTC/TDF).
- HIV infection status (positive, negative, resistance)
- Quality of Life using attached questionnaire
- Adverse reaction related to PrEP treatment

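### The causality scale has a gap: an event with plausible timing, no other cause and PrEP continued meets neither *Possible* nor *Probable*, and no rule says how it is then counted.

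*Protocol*

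**What the plan says.** Section 4.3.4 of the Protocol grades the relationship of an adverse event to study medication as *Unrelated*, *Unlikely*, *Possible*, *Probable* or *Not assessable*. Two grades carry mandatory criteria.

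- *Possible* is headed "Possible (must have first two criteria". The list begins "An adverse event may be considered possible if, or when: (i) it follows a reasonable temporal sequence from administration; (ii) it could readily have been" and continues "produced by the subject's clinical state, environmental or toxic factors, or other modes of therapy administered to the subject; (iii) it follows a known response". Plausible timing and an available alternative cause are therefore both required.
- *Probable* is headed "Probable (must have first three criteria". After timing come the second criterion, "it could not be reasonably explained by the known characteristics of the subject's clinical state", and the third, "iii) it disappears or decreases on cessation or reduction in dose". An exception follows for events that persist after the drug has been discontinued.

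*Unrelated* needs a clear outside cause. *Unlikely* is described through examples: poor timing, a ready alternative cause, no match to the drug's recognised pattern, or no recurrence when the drug is given again. *Not assessable* takes whatever cannot be placed elsewhere.

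Section 4.3.5 defines a SUSAR as "any serious adverse reaction that might be related to the study medication" that is also unexpected, meaning inconsistent with the product characteristics. Section 6 lists "Adverse reaction related to PrEP treatment" among the study variables. The SAP repeats all of this under the same section numbers. Neither document says which grades count as related or how *Not assessable* is tabulated.

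**The concern.** The absence of a competing explanation should raise suspicion of the drug, or at least not lower it. Here it closes off *Possible*. If the drug was also not stopped or reduced, *Probable* is closed too. An event with a competing cause can then carry a causal grade that the otherwise identical event without one cannot.

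What is at stake is the related-reaction summary. It depends on a grade being read as related, and an event labelled *Not assessable* or *Unlikely* can be left out of it. SUSAR screening also turns on relatedness, so the grade may influence it, although less directly.

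Unexpected events deserve particular attention. One *Unlikely* example is lack of fit with the drug's known pattern, and a reaction outside the product characteristics may well meet that description. Such an event has a route to *Unlikely* while *Possible* stays closed for want of another cause.

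**Working it through.** The plan gives no figure on this point, so there is nothing to reproduce. The check applies the mandatory criteria of Protocol 4.3.4 literally to every combination of three facts:

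- timing: plausible or not (2 levels);
- alternative cause: could readily explain the event, or cannot reasonably explain it (2 levels);
- response to stopping or reducing the drug: improved, persisted after stopping, or not tested because PrEP continued (3 levels).

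That gives 2 × 2 × 3 = 12 combinations. For *Unlikely*, the table uses only the timing and alternative-cause examples.

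| Timing | Alternative cause | Response to stopping | Grade whose criteria are met |
|---|---|---|---|
| Plausible | Yes | Any of the 3 | *Possible* (also fits an *Unlikely* example) |
| Plausible | No | Improved | *Probable* |
| Plausible | No | Persisted after stopping | *Probable*, but only through the exception |
| Plausible | No | Not tested, PrEP continued | None, hence *Not assessable* |
| Not plausible | Yes or no | Any of the 3 | *Unlikely* (timing example) |

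The rows account for 3 + 1 + 1 + 1 + 6 = 12 combinations. Exactly one meets no causal grade.

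The reasoning for that one combination is as follows.

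1. *Possible* fails on its second criterion, because there is no alternative cause.
2. *Probable* fails on its third, because improvement off the drug was never observed.
3. The exception to that third criterion concerns events that persist once the drug has been discontinued. It does not reach a drug that was never stopped.
4. *Unrelated* fails, because there is no clear outside cause.
5. The timing and alternative-cause examples of *Unlikely* do not fit. The known-pattern example may fit if the event is unexpected.
6. *Not assessable* remains for the rest.

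Now change one fact in that combination and add a competing cause. The event moves to the first row and meets *Possible*. This is the reversed ordering.

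The gap bears mainly on continuous users. Protocol 5.3 also allows intermittent dosing, and intervals off the drug could show whether an event improves.

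**The case against.** The strongest reply accepts the wording gap and disputes its consequences. Most of that reply stands.

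- **The event is not lost.** Section 4.3.1 has all relevant responses recorded and graded, so the event remains in the records under its label. A reader might infer that Section 6 restricts the analysis to related reactions. It does not: it is a list of variables and specifies no analysis. Omission from the related-reaction variable is a risk left open by the missing mapping, not a stated rule.
- **SUSAR loss is not shown.** The definition in 4.3.5 is broad and names no grade, serious events are defined regardless of relatedness, and 4.3.6 adds a second evaluation that covers causality. These may catch the event. Neither document says whether the second evaluation uses the same scale, so the safeguard can be neither relied on nor dismissed.
- **The strongest drug-caused cases are not the ones affected.** Plausible timing, no other cause and improvement off the drug give *Probable*. The affected combination lacks that last piece of evidence.
- **Not every unexplained fatal event falls in the gap.** PrEP may have been stopped before death, and the exception might then apply.
- **The alternative-cause example of *Unlikely* cannot catch this event**, since by definition it has no other cause. Only the known-pattern example offers a route there.

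It could also be said that the criteria are introduced permissively and leave room for judgement. But the headings make the first two or first three mandatory, and grading around them would vary between investigators.

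**Conclusion.** The concern holds as a defect in a stated rule. One of the 12 combinations has no causal grade, and adding a competing cause to that same event makes *Possible* available. The SAP repeats the scale and does not repair it.

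The consequence is limited. Events of this kind can be left out of the related-reaction variable; loss from SUSAR screening is possible but not established. The one-in-12 figure counts combinations, not events. The documents give no adverse event rates and state the sample size as not applicable, so the undercount cannot be computed and could be zero. The conclusion rests on reading the mandatory criteria literally.

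A correction is worth making because the rule errs in the unsafe direction and costs little to mend. It does not touch the five listed objectives, none of which is safety.

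**What to change.** Change 4.3.4 in both Protocol and SAP, and the eCRF help text to match:

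1. For *Possible*, make only the first criterion (plausible timing) mandatory.
2. Reword its second criterion so that another cause is allowed but not required, for example: *may also be explained by* the subject's condition, surroundings or other therapy.
3. State that plausible timing with no other explanation and no information on stopping or reducing the drug is at least *Possible*.
4. State which grades count as related for the Section 6 variable and for SUSAR screening.
5. Report *Not assessable* as its own line. Counting all such events as related would also sweep in those that merely lack information.

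These are changes to classification wording and leave treatment untouched. The cost is the text revision and a somewhat higher count of related reactions, by an amount the documents do not allow to be estimated. If events have already been graded, those labelled *Unlikely* or *Not assessable* should be looked at again under the revised wording before database lock.
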